In order to maintain patient privacy, all data capture records, drug accountability records, study reports and communications will identify the patient by initials and the assigned patient number. If requested, the investigator will grant monitor(s) and auditor(s) from Millennium or its designees and regulatory authority(ies) access to the patient's original medical records for verification of data gathered on the data capture records and to audit the data collection process. The patient's confidentiality will be maintained and will not be made publicly available to the extent permitted by the applicable laws and regulations.

Investigator Compliance

The investigator will conduct the study in compliance with the protocol given approval/favorable opinion by the IRB/IEC and the appropriate regulatory authority(ies). Changes to the protocol will require approval from Millennium and written IRB/IEC approval/favorable opinion prior to implementation, except when

the modification is needed to eliminate an immediate hazard(s) to patients. The IRB/IEC may provide, if applicable regulatory authority(ies) permit, expedited review and approval/favorable opinion for minor change(s) in ongoing studies that have the approval /favorable opinion of the IRB/IEC. The investigator will submit all protocol modifications to Millennium and the regulatory authority(ies) in accordance with the governing regulations.

On-site Audits

Regulatory authorities, the IEC/IRB and/or Millennium may request access to all source documents, data capture records, and other study documentation for on-site audit or inspection. Direct access to these documents must be guaranteed by the investigator, who must provide support at all times for these activities.

Investigator and Site Responsibility for Drug Accountability

Accountability for the study drug at all study sites is the responsibility of the principal investigator. The investigator will ensure that the drug is used only in accordance with this protocol. Drug accountability records indicating the drug's delivery date to the site, inventory at the site, use by each patient, and amount returned to Millennium or a designee or disposal of the drug (if applicable and if approved by Millennium) will be maintained by the clinical site. Accountability records will include dates, quantities, lot numbers, expiration dates (if applicable), and patient numbers.

Product Complaints

A product complaint is a verbal, written, or electronic expression that implies dissatisfaction regarding the identity, strength, purity, quality, or stability of a drug product. Individuals who identify a potential product complaint situation should immediately contact MedComm Solutions (see below) and report the event.

Whenever possible, the associated product should be maintained in accordance with the label instructions pending further guidance from a Millennium Quality representative.

For Product Complaints, call MedComm Solutions at [contact] ([name]) (US and International)

--

Product complaints in and of themselves are not AEs. If a product complaint results in an SAE, an SAE form should be completed and sent to Millennium Pharmacovigilance.

Closure of the Study

This study may be prematurely terminated, if in the opinion of the investigator or Millennium, there is sufficient reasonable cause. Written notification documenting the reason for study termination will be provided to the investigator or Millennium by the terminating party.

Circumstances that may warrant termination include, but are not limited to:

- Determination of unexpected, significant, or unacceptable risk to patients
- Failure to enter patients at an acceptable rate
- Insufficient adherence to protocol requirements
- Insufficient, incomplete and/or unevaluable data
- Plans to modify, suspend or discontinue the development of the drug.

Record Retention

The investigator will maintain all study records according to the ICH-GCP and applicable regulatory requirement(s).

Use of Information

All information regarding MLN9708 supplied by Millennium to the investigator is privileged and confidential information. The investigator agrees to use this information to accomplish the study and will not use it for other purposes without consent from Millennium. It is understood that there is an obligation to provide Millennium with complete data obtained during the study. The information obtained from the clinical study will be used toward the development of MLN9708 and may be disclosed to regulatory authority(ies), other investigators, corporate partners, or consultants as required.

Upon completion of the clinical study and evaluation of results by Millennium, the hospital or institution and/or investigator may publish or disclose the clinical trial results pursuant to the terms contained in the applicable Clinical Trial Agreement.

Peer Review Statement

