- Tapering of any concomitant acute GVHD prophylaxis will be per institutional guidelines, however in absence of acute GVHD, renal insufficiency and disease relapse/progression it is recommended that taper **SHOULD NOT** commence before day +100. The recommended goal of tapering is the complete discontinuation of immunosuppressive medications by day +180.

Excluded Concomitant Medications and Procedures

The following medications and procedures are prohibited during the study:

Systemic treatment with any of the following metabolizing enzyme inhibitors is not permitted during this study. A DDI with a strong inhibitor would increase MLN2238 exposure.

- Concomitant administration of strong inhibitors of CYP1A2 (fluvoxamine, enoxacin, ciprofloxacin) and strong inhibitors of CYP3A (clarithromycin, telithromycin, itraconazole, voriconazole, ketoconazole, nefazodone, and posaconazole).

Systemic treatment with any of the following metabolizing enzyme inducers should be avoided unless there is no appropriate alternative medication for the patient to use. A DDI with a strong inducer would decrease MLN2238 exposure.

- Strong CYP3A inducers (rifampin, rifapentine, rifabutin, carbamazepine, phenytoin and phenobarbital).
- The dietary supplements St. John's wort and Ginkgo biloba are not permitted.
- Antibiotic prophylaxis will be given according to institutional guidelines. Herpes zoster prophylaxis per institutional guidelines will be required during prophylaxis with MLN9708.
- Patients missing a single dose of MLN9708 (due to decreased oral intake secondary to severe nausea, vomiting, mucositis etc.) should be discussed with study PI. Patients missing >1 dose will need to be replaced. In case MLN9708 therapy is interrupted, the time interval should be recorded.
- Toxicity will be evaluated according to CTCAE v4.0.
- Progression free survival (PFS) and overall survival (OS) following transplantation will be recorded.

Dose modification

- Patients experiencing a grade 3-4 hematological or non-hematological toxicity (as specified in CTCAE v4.0) thought to be related to MLN9708 will be removed from the study permanently (except the exceptions allowed in Table 3). No dose modifications are permitted.

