concluding the new treatment is promising, will be 0.80 (statistical power) when the true but unknown rate of developing chronic GVHD is 30% or 0.04 (type I error) when the true rate is 55% in related donor transplantation (Cohort A [matched sibling donor transplantation] with a sample size of 25). Similarly, the probability of concluding the new treatment is promising, will be 0.81 (statistical power) when the true but unknown rate of developing chronic GVHD is 40% or 0.05 (type I error) when the true rate is 65% in unrelated transplantation (Cohort B [unrelated donor transplantation] with a sample size of 26). The efficacy endpoint is chronic GVHD-free at 1 year and there will be no interim analysis on efficacy for this multi-center study. In the final analysis in Cohort A, if 10 or more of 25 patients have chronic GVHD, we will conclude the new treatment is ineffective in Cohort A; for Cohort B, if 13 or more of 26 patients have chronic GVHD, we will conclude the new treatment is ineffective in Cohort B.

Demographic and baseline laboratory results will be summarized using descriptive statistics, including means with standard deviations, or medians with ranges, histograms and box-plot. The chronic GVHD rate at 1-year and its 95% CI will be calculated by cumulative incidence method, while accounting for competing events. Progression-free survival and overall survival will be estimated using the Kaplan-Meier method.

Cumulative incidence of acute and chronic GVHD, disease relapse and non-relapse mortality will be calculated by accounting for competing events. Competing events for acute GVHD disease are relapse or death without acute GVHD, while those for chronic GVHD are relapse or death without chronic GVHD. Disease relapse and non-relapse mortality are competing events for each other. Toxicity will be reported by type, frequency and severity. Worst toxicity grades per patient will be tabulated for selected adverse events and laboratory measurements. Patients replaced on the protocol (as specified in the Dose Modification Section) will remain evaluable for safety and toxicity assessment.

Safety/Stopping Rules:

For the phase II portion of the study we propose to accrue 51 patients over 24–30 months, which will enroll about 12 patients every 6 month time period. We plan to

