monitor and evaluate short term adverse events at each additional 12 patients who have been enrolled in the study. The expected 100 day post-transplant immunologic graft rejection (defined as less than 5% donor myeloid cells) rate is approximately 2.5% (in absence of relapsed disease) and the enrollment will be put on hold if more than 5% graft rejection rate is seen. For the development of grade 3-4 adverse events deemed to be related to MLN9708, the true rate is 5% and enrollment will be on hold if more than 10% adverse events are observed. The stopping boundaries for graft rejection and development of grade 3-4 adverse events are shown in Table below. In the case of a safety event suspending study, a prompt cumulative examination of all data and circumstances of these events will be conducted by the Medical College of Wisconsin DSMC to determine whether study should be resumed, whether the protocol will be revised or whether the study will be discontinued permanently.

Table. Stopping boundary for adverse events.

Number of patients enrolled	Stopping boundary for immunologic graft-rejection	Stopping boundary for developing grade 3-4 adverse events related to MLN9708
12	≥ 3	≥ 3
24	≥ 3	≥ 4
36	≥ 4	≥ 6
48	≥ 4	≥ 6
51	≥ 5	≥ 7

Accrual Estimate: 6-12 patients will be enrolled in the phase I part of the protocol. In the phase II portion a total of 52 patients (25 sibling and 27 unrelated donor transplantation) will be enrolled, with 1-3 per month. Total estimated accrual = 58 patients.

Accrual Period : Approximately 24-30 months

Follow-Up Period : Two years to evaluate incidence of acute and chronic GVHD and relapse pattern, and five years for survival outcomes.

10. Adverse Event Reporting Requirements

11. Definitions

The following are definitions of adverse events as defined by 21CFR312.32.

Types of Adverse Events

Adverse Event (AE) means any untoward medical occurrence associated with the use of a drug in humans, whether or not consider drug related. An AE can therefore be any unfavorable and unintended sign (including an abnormal laboratory finding), symptom, or disease temporally associated with the use of a medicinal (investigational) product whether or not it is related to the medicinal product. This includes any newly occurring event, or a previous condition that has increased in severity or frequency since the administration of study drug.

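### Dosed phase II patients who are replaced or removed appear to leave the primary count of 25 or 26 for post-dosing reasons, and no efficacy population is defined.

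*Combined protocol and SAP*

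**What the plan says.** Three sets of statements bear on who is counted.

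- **Replacement.** The missed-dose bullet in Section 5, just before Dose modification, says "Patients missing >1 dose will need to be replaced". Its example of a missed dose is one "due to decreased oral intake secondary to severe nausea, vomiting, mucositis etc". It is not limited to phase I.
- **Removal.** Dose modification says that patients with a grade 3-4 toxicity "thought to be related to MLN9708 will be removed from the study permanently", apart from the Table 3 exceptions. Duration of therapy lists related grade 3-4 toxicity as a reason to end MLN9708. It also lists grade III-IV acute GVHD and severe chronic GVHD.
- **Analysis.** Section 9 says: "Patients replaced on the protocol (as specified in the Dose Modification Section) will remain evaluable for safety and toxicity assessment". It does not mention efficacy for these patients. A cohort is declared ineffective on a count: "In the final analysis in Cohort A, if 10 or more of 25 patients have chronic GVHD", and "for Cohort B, if 13 or more of 26 patients have chronic GVHD".

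No section defines an efficacy population. For Cohort B, Section 9 states "0.05 (type I error) when the true rate is 65% in unrelated transplantation" with a sample size of 26. The Protocol Summary and the Accrual Estimate both say that "a total of 52 patients (25 sibling and 27 unrelated donor transplantation) will be enrolled".

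**The concern.** Missing doses through poor oral intake and having a drug-related toxicity both happen after dosing starts. If such patients are refilled and counted for safety only, the primary rate describes patients who tolerated most of the course, while the 55% and 65% null rates are given for the whole transplant groups. The trial has no control arm in which the same selection would occur. Each cohort also turns on one patient: 9 versus 10 of 25, or 12 versus 13 of 26.

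The wording leaves three further questions open:

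- Section 9 says that replacement is specified under Dose modification, but that part only removes or holds. The replacement sentence is in the bullets before it. The cross-reference suggests that patients removed for toxicity are among those replaced, without saying so.
- Removal from the study sits badly with the 1-year chronic GVHD assessment, whereas Duration of therapy treats the same toxicity as ending drug only.
- Dosing is weekly and a hold of up to 14 days is allowed, so a permitted hold or a protocol-required stop can leave more than one dose untaken. Whether that counts as missing is not stated.

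**Working it through.** **Inputs (Section 9).** Null rates p0 = 0.55 (A) and 0.65 (B). Alternatives p1 = 0.30 and 0.40. Promising if at most 9 of 25 (A) or at most 12 of 26 (B) have chronic GVHD. Below, F(c; n, p) is the binomial probability of c or fewer events in n, and f(c; n, p) is the probability of exactly c.

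**1. The plan's own figures.**
- A: F(9; 25, 0.55) = 0.0440 and F(9; 25, 0.30) = 0.811. Stated: 0.04 and 0.80.
- B: F(12; 26, 0.65) = 0.0377 and F(12; 26, 0.40) = 0.801. Stated: 0.05 and 0.81.

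Both powers agree within about one point. A's alpha agrees. B's stated 0.05 holds only as an upper limit.

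**2. One patient with chronic GVHD dropped and refilled at the null rate.** The cohort now also passes when the original count was one too many and the refill is free of chronic GVHD. Alpha = F(c; n, p0) + (1 − p0) × f(c+1; n, p0).
- A: 0.0440 + 0.45 × 0.0520 = 0.067
- B: 0.0377 + 0.35 × 0.0455 = 0.054

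**3. One patient free of chronic GVHD dropped and refilled at the null rate.** Alpha = F(c−1; n, p0) + (1 − p0) × f(c; n, p0).
- A: 0.0174 + 0.45 × 0.0266 = 0.029
- B: 0.0150 + 0.35 × 0.0227 = 0.023

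**4. A share s of dosed patients excluded, with chronic GVHD rate r.** The retained rate is q = (p0 − s·r)/(1 − s). If r = p0, then q = p0 and alpha is unchanged. The documents give neither s nor r. The values below are assumptions. The 5% and 10% are borrowed from the related grade 3-4 figures in Safety/Stopping Rules; the rates r have no source in the documents.

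| Cohort | r | alpha, s = 5% | alpha, s = 10% |
|---|---|---|---|
| A | 0.40 | 0.037 | 0.030 |
| A | 0.55 | 0.044 | 0.044 |
| A | 0.75 | 0.055 | 0.069 |
| B | 0.50 | 0.031 | 0.025 |
| B | 0.65 | 0.038 | 0.038 |
| B | 0.85 | 0.048 | 0.062 |

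With 25 or 26 left after replacement, these shares mean 1.3 to 2.8 exclusions in A (25/0.95 − 25; 25/0.90 − 25) and 1.4 to 2.9 in B (26/0.95 − 26; 26/0.90 − 26).

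**5. Cut-offs by final n.** Largest c with F(c; n, p0) ≤ 0.05.

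| Cohort | n | Promising if ≤ | alpha | power |
|---|---|---|---|---|
| A | 25 | 9 | 0.044 | 0.81 |
| A | 26 | 9 | 0.029 | 0.77 |
| A | 27 | 10 | 0.046 | 0.84 |
| A | 28 | 10 | 0.032 | 0.81 |
| B | 26 | 12 | 0.038 | 0.80 |
| B | 27 | 12 | 0.023 | 0.75 |
| B | 28 | 13 | 0.034 | 0.81 |
| B | 29 | 14 | 0.048 | 0.86 |

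For B at n = 27, a cut-off of 13 gives alpha 0.054 and power 0.86, so it exceeds 0.05.

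**6. Power if one replaced patient is kept and carries the null risk.** Power = (1 − p0) × F(c; n, p1) + p0 × F(c−1; n, p1).
- A, final n = 26, cut-off 9: 0.45 × 0.811 + 0.55 × 0.677 = 0.74
- B, final n = 27, cut-off 12: 0.35 × 0.801 + 0.65 × 0.674 = 0.72

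**The case against.** The strongest reply is that the plan is not truly silent. A replaced patient's place goes to someone else, and Section 9 keeps that patient for safety and toxicity and lists nothing more. On that view the plan has chosen an evaluable population, and the request is only to say so. This stands in part: exclusion is the natural reading. It does not remove the point, because on that same reading patients leave the count for post-dosing reasons.

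A reader might infer that the plan inflates type I error. The documents do not support that. They give no replacement rate and no chronic GVHD rate for excluded patients, and alpha can rise, stay the same or fall. Steps 2 and 3 fix the dropped patient's outcome, so they mark out a range and are not a forecast. At a 5% share, even the adverse rows move alpha only to 0.055 (A) and 0.048 (B), the latter within B's stated 0.05. Removal for chronic GVHD itself is also unlikely during dosing, since the eligibility criteria call active chronic GVHD unlikely before day +100.

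A reader might also infer that who counts could be chosen once 1-year outcomes are known. That is unlikely. Replacement is mandatory and turns on a dose count. With a latest start at day +90, the fourth dose falls near day +111 (90 + 21), apart from holds, which is months before the endpoint.

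Nor is it established that removed patients lose their 1-year assessment. The visit schedule in Sections 6 and 7 makes no exception for patients off drug.

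The Cohort B discrepancies exist whatever happens to replaced patients and add no weight to the population question.

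**Conclusion.** The point holds as a defect in who is counted, with the direction of bias unknown. That dosed patients leave the primary count is inferred from Sections 5 and 9 together; neither states it. Changing the fate of one patient moves alpha from 0.044 to between 0.029 and 0.067 in Cohort A, and from 0.038 to between 0.023 and 0.054 in Cohort B. It has no effect on alpha if excluded patients carry the null risk. The sizes rest on an assumed outcome for the excluded patient and on a refill at the null rate.

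Two separate facts need no such assumption. Cohort B has a rule for 26 but enrols 27 with no cut-off given, and its exact alpha at 26 is 0.038, not 0.05.

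**What to change.** 1. Define the primary efficacy population as all phase II patients who took at least one dose, including those later stopped, removed or replaced. Keep patients who completed dosing as a sensitivity analysis. State how death, relapse or loss to follow-up before 1 year enters the binomial count; Section 9 treats relapse and death as competing events only for cumulative incidence.
2. Reconcile the missed-dose bullet, Dose modification, Duration of therapy and Section 9 on three matters: off drug versus off study, whether removed patients are replaced, and whether held or protocol-stopped doses count as missed. The result should leave patients off drug with the chronic GVHD assessment already scheduled at 1 year.
3. State the exact cut-off, alpha and power for the final n in each cohort, as in step 5 of the working. For Cohort B, settle 26 or 27 and restate alpha at n = 26 as 0.038.

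**Cost.** No new visits. There is a real cost in power if early stoppers carry the null risk: with one replaced patient kept, power is 0.74 in A (n = 26) and 0.72 in B (n = 27), against 0.81 and 0.80 now. The sponsor would have to accept that or choose a final n with a better cut-off.

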- If a patient experiences a Grade 3 or 4 non-drug-related renal function impairment or hepatic function impairment, MLN9708, can be held until recovery to Grade 1 or baseline (up to a maximum of 14 days). Upon recovery of the toxicity to a level allowing continuation of therapy, a dose reduction is not necessary.

Duration of therapy

MLN9708 will be continued until any one of the following criteria is met:

- Patient finishes four doses of MLN9708.
- Patient develops grade III-IV acute GVHD.
- Patient develops severe chronic GVHD.
- Patient develops any grade 3-4 toxicity related to MLN9708 use.

Data Safety Monitoring Plan

The Medical College of Wisconsin (MCW) Cancer Center (CC) Data Safety Monitoring Committee (DSMC) is responsible for monitoring data quality and subject safety for all cancer center investigator initiated clinical trials. A six to eight member Data and Safety Monitoring Committee will complete a review of protocol-specific data safety monitoring reports, to provide recommendations on trial continuation, suspension or termination.

A summary of the MCW CC DSMC activities are as follows:

- Review the clinical trial for data integrity and safety
- Review all unexpected grade 3, and all grade 4, and 5 adverse events, as well as any others requiring expedited reporting as defined in this protocol. (Grades 4 & 5 events must be reported to the DSMC within 5 calendar days of study staff's knowledge.)
- Review all DSMC reports
- Submit a summary of any recommendations related to study conduct
- Terminate the study if deemed unsafe for patients

A copy of the MCW CC Data and Safety Monitoring Plan and membership roster will be maintained in the study research file and updated as membership changes. The committee will

review reports from the study PI twice annually (or more frequently if needed) and provide recommendations on trial continuation, suspension or termination as necessary.

Any available DSMC letters will be submitted to the IRB of record as required.

6. Measurement of Effect:

Follow up schedule:

The schedule for follow up on the study is shown in the table below.

Study Visit	Approximate target Day Post-Transplant
1	60 days
2	67 days
3	74 days
4	81 days
5	90-100 days
6	180 days
7	365 days
8	2 years

Patients will be followed for survival, relapse and cause of death for 5 years post transplantation.

Phase I patients will be seen weekly for toxicity assessment during the DLT period.

GVHD Assessment:

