At the time of enrollment and/or first dose of MLN9708 patients will be graded for acute and chronic GVHD. Subsequently patients will be monitored for development of acute and chronic GVHD approximately once a week until day +100. After Day 100, patients will be assessed at each study visit for the presence of GVHD. Diagnosis of acute GVHD will ideally require biopsy confirmation in at least one involved organ. When more than one organ is involved, biopsy confirmation of all involved organs is recommended but not necessary. Liver-only GVHD must be confirmed by biopsy. Acute GVHD will be assessed by consensus criteria (Appendix A)⁵⁷ and graded on BMT CTN MOP suggested grading sheets (Appendix A). Acute GVHD assessment and grading will be performed by **treating physicians**. Chronic GVHD diagnosis and grading will be according to NIH Criteria. Please see Appendix B^{58, 59}.

Clinical Grading of Chronic GVHD (According to Appendix B)

None

Mild chronic GVHD involves only 1 or 2 organs or sites (except the lung: see below ‡), with no clinically significant functional impairment (maximum of score 1 in all affected organs or sites)

Moderate chronic GVHD involves: (1) at least 1 organ or site with clinically significant but no major disability (maximum score of 2 in any affected organ or site) or (2) 3 or more organs or sites with no clinically significant functional impairment (maximum score of 1 in all affected organs or sites). ‡A lung score of 1 will also be considered moderate chronic GVHD.

Severe chronic GVHD indicates major disability caused by chronic GVHD (score of 3 in any organ or site). ‡A lung score of 2 or greater will also be considered severe chronic GVHD.

Presence of limited or extensive chronic GVHD will be also be recorded.

Chimerism Assessment and Immune Reconstitution:

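### Taken literally, the removal and replacement rules can drop the 1-year chronic GVHD outcome of patients who did not tolerate MLN9708, so the decision may rest on patients selected for tolerance.

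*Combined protocol and SAP*

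**What the plan says.** Four places bear on this.

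- **Section 5, Dose modification.** A patient with a related grade 3-4 toxicity "will be removed from the study permanently (except the exceptions allowed in Table 3").
- **Section 5, Duration of therapy.** The reasons to stop MLN9708 include "Patient develops any grade 3-4 toxicity related to MLN9708 use". Here the consequence is the end of dosing; leaving the study is not mentioned.
- **Section 5, list under Excluded Concomitant Medications and Procedures.** "Patients missing >1 dose will need to be replaced".
- **Section 9.** "Patients replaced on the protocol (as specified in the Dose Modification Section) will remain evaluable for safety and toxicity assessment". Efficacy is not mentioned. The Dose modification subsection to which this sentence points holds the removal rule but no replacement rule.

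The sibling decision reads: "if 10 or more of 25 patients have chronic GVHD, we will conclude the new treatment is ineffective in Cohort A". The unrelated-donor rule has the same form, with 13 or more of 26. Section 9 does not define which patients make up the 25 and 26.

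The follow-up text is not conditional on dosing. Section 6 says "After Day 100, patients will be assessed at each study visit for the presence of GVHD", and the Section 7 calendar marks chronic GVHD assessment at days 180, 365 and 730.

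**The concern.** Removal and replacement both happen after dosing, and the drug can cause both. If a patient taken off for toxicity is no longer assessed, that patient's 1-year outcome is unobserved. If a patient is replaced and kept for safety only, the outcome may be observed but not counted. Either way the efficacy count can come to describe patients who tolerated the drug rather than patients who were given it.

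Each cohort is a single arm judged against a fixed rate (55% for siblings, 65% for unrelated donors), so there is no control arm subject to the same selection. If patients who stop for toxicity differ in chronic GVHD risk from those who continue, the observed count shifts against that fixed rate for a reason unrelated to efficacy.

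**Working it through.** **1. The plan's own design.** Inputs from Section 9: siblings (A) n = 25, null 55%, alternative 30%, promising if X ≤ 9; unrelated donors (B) n = 26, null 65%, alternative 40%, promising if X ≤ 12. X is the number with chronic GVHD, exact binomial.

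| | Type I error | Power |
|---|---|---|
| A | P(X ≤ 9; 25, 0.55) = 0.044 (stated 0.04) | P(X ≤ 9; 25, 0.30) = 0.811 (stated 0.80) |
| B | P(X ≤ 12; 26, 0.65) = 0.038 (stated 0.05) | P(X ≤ 12; 26, 0.40) = 0.801 (stated 0.81) |

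These figures hold if every counted patient is an unselected dosed patient with a known outcome.

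**2. Which toxicity stops trigger replacement.** Of four doses, stopping after dose 1 misses 3 and stopping after dose 2 misses 2, so the replacement rule applies. Stopping after dose 3 misses 1 and after dose 4 misses 0, so it does not. The last two groups are removed but not replaced, and Section 9 has no sentence for them.

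**3. How often it may arise.** The Safety/Stopping Rules say of related grade 3-4 events that "the true rate is 5% and enrollment will be on hold if more than 10% adverse events are observed". Taking 5% as a per-patient rate (an assumption; it also includes events exempt under Table 3), the expected number is 25 × 0.05 = 1.25 in A and 26 × 0.05 = 1.30 in B. The chance of at least one is 1 − 0.95^25 = 0.72 and 1 − 0.95^26 = 0.74. At the 10% hold threshold these chances are 0.93 and 0.94.

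**4. Illustration of selection.** Suppose a fraction d of dosed patients is removed and replaced by patients who tolerate the drug. Let q be the chronic GVHD rate in those removed, and let the rate over all dosed patients equal the null p0. The counted patients then have rate r = (p0 − d·q)/(1 − d). The documents give no value for q, so every q below is assumed.

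| d | q | A: r | A: type I error | B: r | B: type I error |
|---|---|---|---|---|---|
| any | equal to p0 | 0.550 | 0.044 | 0.650 | 0.038 |
| 5% | 80% | (0.55 − 0.04)/0.95 = 0.537 | 0.058 | (0.65 − 0.04)/0.95 = 0.642 | 0.045 |
| 10% | 80% | (0.55 − 0.08)/0.90 = 0.522 | 0.077 | (0.65 − 0.08)/0.90 = 0.633 | 0.055 |
| 10% | 30% (A), 40% (B) | (0.55 − 0.03)/0.90 = 0.578 | 0.023 | (0.65 − 0.04)/0.90 = 0.678 | 0.018 |

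If removed patients have the average risk, nothing changes. If their risk is higher, type I error rises; if lower, it falls. The documents do not say which case applies. Because only stops after dose 1 or 2 trigger replacement, the fraction actually replaced for toxicity would be smaller than the fraction with an event.

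**5. Cost of counting all dosed patients.** If 5% are under-dosed and get no benefit, the rate under the alternative becomes 0.95 × 0.30 + 0.05 × 0.55 = 0.3125 in A and 0.95 × 0.40 + 0.05 × 0.65 = 0.4125 in B. Power is P(X ≤ 9; 25, 0.3125) = 0.770 and P(X ≤ 12; 26, 0.4125) = 0.762. Type I error is unchanged, because under the null the under-dosed have the same rate as the rest.

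**The case against.** The best reply is that the plan already answers most of this. Duration of therapy treats the toxicity as a drug stop; the visit schedule, the GVHD assessment text and the calendar apply to patients without regard to dosing. Removal may therefore mean off treatment only. A reader might infer that the plan intends to stop assessing these patients, and the documents do not support that: there is a loose sentence and an unconditional calendar, and the two have not been reconciled.

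Nor is the handling of replaced patients blank. Replacing someone while keeping that person for safety ordinarily means that the replacement takes the efficacy slot. That reading is fair, and a replacement rule is defensible in a single-arm activity trial. It is also the reading under which the efficacy set is selected on tolerance, so it does not remove the concern.

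A reader might also infer that the plan biases the result towards success. It may not: replacements of equal risk leave type I error and power unchanged, and no text links toxicity to chronic GVHD risk. Nor is it evidence of harm that the verdict in a cohort of 25 or 26 can turn on one or two patients. That holds for any patient under any such rule, whether removed for toxicity or not.

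Finally, making all dosed patients the primary set would override the replacement rule and cost power, more so if under-dosing exceeds 5%. At an assumed 10% without benefit, the rates are 0.325 and 0.425 and power is 0.727 (A) and 0.719 (B). This stands, and it is why the choice of primary set is left open below.

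**Conclusion.** The point holds as a defect of specification with a possible, unquantified selection effect. On a literal reading, the removal sentence ends participation for an event that another subsection treats only as a drug stop, and the one analysis sentence on replaced patients names only safety and toxicity. Patients who did not tolerate MLN9708 can thus be missing from, or left out of, the 9-of-25 and 12-of-26 decisions.

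The situation is likely to arise: at the protocol's 5% rate, read per patient, there is a 72-74% chance of at least one such event per cohort. The consequence depends on a link between toxicity and chronic GVHD risk that the documents neither give nor exclude. The type I errors of 0.077 and 0.055 show what one assumed link would do (10% removed and replaced, 80% chronic GVHD among them); they are not estimates. The correction is worth making before outcomes are known, because a later choice of who counts could depend on the data.

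**What to change.** 1. In Dose modification, replace removal from the study with permanent discontinuation of MLN9708. State that chronic GVHD, relapse and survival assessments continue on the existing calendar for every dosed patient. Apply the Table 3 exceptions in the same words in Duration of therapy.
2. In Section 9, state which patients make up the 25 and the 26. Report the decision on all dosed patients (the first 25 and first 26, same cutoffs) alongside the set with replacements, and name one as primary in advance. Which one is the sponsor's choice.
3. Do not add replaced patients on top under unchanged cutoffs. One extra patient gives type I error and power of 0.029 and 0.770 in A (n = 26), and 0.023 and 0.750 in B (n = 27). This matters for B because the accrual estimate already plans "52 patients (25 sibling and 27 unrelated donor transplantation) will be enrolled", one more unrelated-donor patient than the rule uses.
4. Point the Section 9 sentence on replaced patients to the list that holds the replacement rule.

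**Cost.** The follow-up change is wording only, since the day 180, 365 and 730 assessments are already scheduled. The second analysis needs no new data. If all dosed patients are primary, power is about 0.77 (A) and 0.76 (B) when 5% are under-dosed without benefit, with type I error unchanged.
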